1 PROTOCOL SUMMARY

1.1 SYNOPSIS

- Title:** Acute effects of medium chain triglyceride (MCT) nutritional ketosis on Parkinson's Disease (PD) symptoms and biomarkers (MCT-PD)
- Study Description:** While three pilot studies of ketogenic diet (KD) in PD have shown either reduction in motor scores (UPDRS) or improved memory/fluency cognitive testing, there are gaps in knowledge of the time course and mechanisms of reported outcomes. Furthermore, only a standard ketogenic diet was studied while there are variations such as MCT oil supplementation shown to increase keto-induction, and other adaptations may improve tolerability and micronutrient content. It is the goal of this proposed inpatient metabolic study to address the initial question of effect size and time course of ketosis. If suggestive of benefit in PD, this pilot study may lead to a subsequent larger study of long-term feasibility and effects on disease biomarkers and disease progression, which might also compare alternate diets of interest in PD such as Mediterranean diet. Thus, a pilot feasibility study is proposed, targeting retention rate >80% and adherence in the outpatient setting. Recruitment of 32 participants is based upon power analysis of secondary outcome, testing the Timed Up & Go mobility test that has reported validity in fall prediction, additionally plotting continuous and serially repeated direct/indirect ketosis measurements and motor as well as non-motor symptoms / exploratory disease biomarkers. It is hypothesized that, compared to a non-ketogenic, standard American diet (SAD, also referred to interchangeably as usual diet, see Section 2.1 table for description), ketogenic diet supplemented by MCT oil (MCT-KD) will improve mobility tested by Timed Up & Go (TUG), as well as akinesia, tremor, and memory/executive function tasks, and will reduce motor and non-motor fluctuations within the acute period of keto-induction and early ketogenic timepoints due to improved mitochondrial function and neurotransmitter signaling.
- Objectives:** The primary objective is to test the hypothesis that nutritional ketosis (NK) supplemented by MCT oil in a PD cohort (MCT-KD) is feasible for a duration of three weeks. The secondary objective is to show that NK improves PD symptomatology in cognition (improved attention, recall, and executive function), mobility (TUG), and motor function (bradykinesia, akinesia and tremor) within three weeks.
- Outcomes:** The primary outcome is feasibility, as determined by a composite outcome of recruitment and retention, acceptability and adherence, including full recruitment to study target of 32 participants; completion rate >80% in both inpatient 1-week and outpatient 2-week segments; adherence in the outpatient segment of estimated low carbohydrate diet <10% mean total

Abbreviated Title: Feasibility and efficacy of ketogenic diet in Parkinson's Disease

Version Date: 04/19/2021

daily energy defined as net carbs); and acceptability defined via exit survey (week 3) 4-point Likert efficacy and likelihood scales on how effective ketogenic diet appears on symptoms and how likely ketogenic diet, with or without MCT oil, participants estimate they will continue the diet on at least an intermittent basis in the future.

The secondary outcome is Timed up & go (TUG) mean difference between groups at the end of admission (day 7).

Exploratory outcomes include both group comparisons (mean difference) at day 7 and repeated measures days 1-7 between MCT-KD and SAD groups (in most but not all outcomes; refer to section 1.3 Schedule of Activities for details) and at week 3, when both groups combine to a single ketogenic diet group, and within-group pre vs. post intervention comparisons at 1 & 3 weeks for both groups separately (SAD at 0 & 2 weeks of ketogenic diet vs. MCT-KD group at 1 & 3 weeks, respectively) and all participants, in the following: Stroop word-color interference latency (executive function), n-back recall task (attention and working memory), finger tap speed and rhythm (MN and PQ keyboard tasks), accelerometry amplitude for tremor analysis; 9-hole pegboard test (9-HPT) (daily), heart rate variability HF power, total power (resting, daily), cardiovagal testing via deep breathing and Valsalva Maneuver (pre vs. post), mean subjective on vs. off time (pre vs. post), non-motor severity score (NMSS) pre vs. post, keto-induction symptoms, UPDRS (pre vs. post), EEG spectral power by frequency and connectivity analysis (day 1 vs. day 7 vs. week 3), Geriatric Depression Scale (GDS, pre vs. post)

Study Population:

Idiopathic Parkinson's Disease of moderate severity, Hoehn & Yahr Stage 2-4, age >50, usual (carbohydrate predominant) diet at baseline. A total of 32 PD patients will be recruited predominantly from the Parkinson's Clinic at NIH and local sites given necessity of three visits to facilitate randomization and baseline data acquisition. Recruitment will continue as per power analysis for Timed Up & Go (TUG).

Phase:	1
Description of Sites/Facilities	Enrollment will occur at Screening Visit, NIH Clinical Center Outpatient Clinic 5 (OP5). Admission will occur at NIH Clinical Center Metabolic Unit, 7SW.
Enrolling Participants:	Unit, 7SW.
Description of Study Intervention:	The study intervention is randomization to MCT-KD (ketogenic diet with 80% energy from lipids including Liquigen® (KetoCal) comprising 25% of the daily lipid energy divided twice daily or typical, standard American diet (SAD) x 6 days, followed by 2 weeks ketogenic diet in both groups at home. The proposed diets are isocaloric and have the same ratio of protein (10-15% daily energy) with similar mealtime boluses to limit differences in L-DOPA absorption. Daily activity and exercise plans will be individualized upon admission including use of stationary bike, aiming to maintain baseline levels. Diet with MCT oil will begin on hospital day 2

[figure not shown]
Abbreviated Title: Feasibility and efficacy of ketogenic diet in Parkinson’s Disease

Version Date: 04/19/2021

and be provided to both groups at outpatient day 1 Both diets will be double-blinded (combination of shakes and similar appearing snacks). MCT-KD will feature reduced carbohydrate intake of 5-10% daily energy requirement calculated in the Metabolic Unit. Safety monitoring will be performed by IMM.

Study Duration: 9 months
Participant Duration: 3 weeks

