4. STUDY DESIGN

4.1 OVERALL DESIGN

The experiment will take place predominantly in the Metabolic Unit, 7SW-S (1-week inpatient) and at home (2 weeks outpatient). Additionally, EEG, TUG, and heart rate variability tests will be performed in the HMCS labs within the 7SW-Neurotesting area.

This study is a single center (NIH Clinical Center), phase 1 feasibility/tolerability assessment of MCT oil subtype of ketogenic diet in a PD cohort, randomized, double-blinded vs. standard American (high-carbohydrate) diet based on macronutrient percentages of calculated daily energy expenditure using measured pCO₂ and pO₂ and Weir formula for indirect calorimetry, performed on screening visit, to give caloric macronutrient ratios 50-55% carb, 35% lipid, 10-15% protein in SAD group and 5-10% carb, 80% lipid, 10-15% protein in MCT-KD group on the 7SW-S Metabolic Unit with assistance of CC Nutrition Department staff. Consent, baseline lipid panel, BMP, and pregnancy test will be done at screening visit. Randomization will occur upon screening visit, stratified by age ≥ 65 or < 65 and baseline TUG score ≥ 11.5 s or < 11.5 s. Protein macronutrient percentage of individual calculated daily energy intake will be the same between the two groups. Diet will be within subject factor for both groups, as pre-diet intervention baseline testing is planned for hospital day #1. The potential confound of changes in activity/exercise level while in the hospital on physiologic and clinical outcomes is recognized. To address this, study investigators will form an individualized exercise plan incorporating baseline exercise and activity levels to involve stationary bike at target HR based on age-adjusted HR max target using Tanaka's formula validated in the elderly population, $208 - 0.7 \times \text{age}$, in order to approximate each participant's daily baseline intensity levels from questionnaires.

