The interventional food-based product, Liquigen® (KetoCal), will be administered by NIH CC Nutrition staff to MCT-KD group participants as per defined blinded diet.

Primary Outcome: feasibility will be assessed in a composite fashion by retention rate >80% at study end (week 3) ; study adherence in the outpatient segment defined by maintaining mean carbohydrate limit ≤ 10%, as by CC nutrition staff twice weekly unscheduled calls data input to online application); reaching recruitment target of 32 participants, unless otherwise defined by interim analysis (see Section 9); and acceptability by likelihood to use the diet in the future and effectiveness in reducing PD symptoms both “somewhat” ≥ 2/4 on Likert scales. All criteria must be met.

Secondary outcome: Timed Up & Go (TUG) time at between MCT-KD and SAD groups mean difference on inpatient day 7.

Exploratory outcomes:

Effort will be taken in establishing medication and testing schedules, for outcomes to be assessed at the same time from last dopaminergic medications and other psychotropic medication administrations including cholinergic and muscle relaxants (see table 2). All exploratory outcomes will be assessed pre (admission day 1) and post (day 7 and week 3) diet intervention. Additionally, reaction time, Stroop test, N-back test, MN/PQ fingertapping tests, 9-HPT, UPDRS-3, and resting HRV will be tested daily on admission days 2-6.

Stroop word color interference latency (Stroop test B), N-back test (3-back letter), MN and PQ keystroke tasks, tremor accelerometry, 9-hole pegboard test (9-HPT), and simple reaction time (SRT), EEG waveform analysis (steepness ratio, sharpness ratio, modulation index), and quantitative (q)EEG assessment; daily assessments of heart rate variability (SDNN, pNN50, rMSSD, power spectral analysis), and supine to standing blood pressure and heart; resting heart rate (5 min recordings daily), UPDRS including daily UPDRS-3, daily ON time, daily PD symptoms, daily keto-induction symptoms, pre vs. post intervention Non-Motor Symptom Severity Score (NMSS)

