Of methodological importance, a learning effect is expected in repeated tests, more so in the proposed tests involving preparation and decision such as Stroop word-color interference, TUG, and 3-back recall. However, the underlying assumption of learning effect is that it is expected to be equivalent in both randomized study conditions, and moreover is of study interest for between-group effect though not directly measured. The tests were selected as ones with established reliability of repeated testing, which is operationally validated for simple motor tasks - simple reaction time (18 trials, Hamsher 1977), 9-hole pegboard test, MN-PQ keyboard tapping speed, and TUG. On the other hand, there is greater potential learning bias in cognitive tasks, particularly visuo-verbal 3-back working memory task (Soveri et al 2018) where test-retest reliability has been reported as moderate, whereas simple reaction time reliability is much higher. Nonetheless, it is the aim to adjust for learning effect by randomization between the groups stratified by age. Learning effect could account for some of the difference in performance between the groups particularly in cognitive tasks. The goal is to capture which types of testing improve, whether ones more (n-back test, Stroop word-color interference) or less (reaction time, tapping speed, TUG) subject to learning effect, to infer appropriately whether or not learning effect may be considered to be operative in any difference between the groups.

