Overview of Trial Flow and Events. Figure 1 highlights MCT-KD trial flow and events. We propose a screening enrollment of 1-2 participants per week for total of 32 participants. Upon meeting study criteria and consent, participants are asked to provide one week baseline diet and activity/exercise intake, and then be admitted to NIH CC for a one week study intervention assessing ketosis and symptom outcomes, safety monitoring and potential biomarkers of the diet on Parkinson's EEG and BDNF levels. During admission and discharge, communication will be maintained with participants regarding the requested outpatient portion, in which participants are provided meal plans to continue (or in the case of standard diet participants, begin) a standard ketogenic diet, with MCT oil in the home. The outpatient diet will be given as recommended meals and instructions to be reachable via telephone for twice weekly unscheduled calls from NIH CC Nutrition staff to populate diet adherence using diet tracking linked to study investigator's account. Additionally, study nutritionist / investigator (not involved in study rating) will perform unscheduled twice weekly phone calls to obtain post-screening baseline diet (one week) and outpatient KD intervention adherence assessment (two weeks). Participants will then be asked to return for a follow-up visit in NIH CC OP5 two weeks after discharge date. If the appointment date varies from two weeks for any reason, the same visit and measurements will occur, but visits will be demarcated separately for statistical analysis.

Abbreviated Title: Tolerability and efficacy of ketogenic diet in Parkinson's Disease

Version Date: 04/19/2021

Screening procedure: Following recruitment, potential subjects will be pre-screened by telephone, in person, or via email communication according to the inclusion / exclusion criteria, discussion of the scope of the study and study design, expected potential benefits and side effects. If the potential candidate meets the study eligibility criteria, a screening visit will be scheduled at NIH CC outpatient clinic. The estimated duration of the screening visit is 4 hours, and may be spread over 2 separate days if necessary. Upon registration, an order will be submitted for metabolic tracking (PCO₂:PO₂ gas exchange) for calculation of daily resting energy expenditure.

Informed consent will be obtained prior to any tests or procedures being conducted at the screening visit.

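### The exploratory pre/post comparisons use day 1 as the pre visit in both arms and, on the natural reading, pool everyone at week 1, although control participants start the ketogenic diet only after day 7

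*Combined protocol and SAP*

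**What the plan says.** Besides the between-arm contrasts, the Outcomes paragraph of section 1.1 lists "within-group pre vs. post intervention comparisons at 1 & 3 weeks for both groups separately". It then sets out each arm's exposure at those two times and adds a pooled group: "SAD at 0 & 2 weeks of ketogenic diet vs. MCT-KD group at 1 & 3 weeks, respectively) and all participants".

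Section 4.1 fixes the reference visit: "All exploratory outcomes will be assessed pre (admission day 1) and post (day 7 and week 3) diet intervention". It also states: "Diet will be within subject factor for both groups, as pre-diet intervention baseline testing is planned for hospital day #1". Neither statement distinguishes the arms.

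The SAD arm has no ketogenic diet in hospital. Section 1.1 says the diet with MCT oil will start on hospital day 2 "and be provided to both groups at outpatient day 1". Section 6.1.1 says the outpatient plans let participants continue ("or in the case of standard diet participants, begin) a standard ketogenic diet").

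Section 4.2 says "a learning effect is expected in repeated tests" and gives the remedy: "Nonetheless, it is the aim to adjust for learning effect by randomization between the groups stratified by age".

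Section 9.4.3 tests the diet effect by ANCOVA with age and the day-1 value as covariates, and names longitudinal models for change over the six days. It gives no method for the within-arm or pooled pre/post comparisons.

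**The concern.** A pre/post comparison measures an intervention only if the pre visit comes just before the intervention and nothing else changes. Neither holds for SAD between day 1 and day 7. These participants move into hospital, follow an individual exercise plan, eat the standard diet and repeat most of the tests daily, but receive no ketogenic diet.

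Two comparisons therefore do not match their label. The all-participants comparison at week 1 mixes 16 people on the ketogenic diet with 16 who have not started it. The SAD comparison at week 3 starts from a visit that precedes the six-day standard diet, and the pooled week-3 comparison inherits this.

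Section 1.1 says the trial should inform a later study on effect size and time course. Hypothesis B in section 9.1 predicts larger exploratory effects at 3 weeks than at 7 days. At week 3 both arms are on the ketogenic diet, so no unexposed control remains and readings there lean on these pre/post changes. Accumulating practice could look like support for Hypothesis B.

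**Working it through.** **1. The plan's own figure.** Section 9.2 uses a difference of 4.5 s and an SD of 4 s (4.5/4 = 1.125) at two-sided 0.0492. The noncentral t gives power of 78.4% at 13 per group and 81.5% at 14, hence 28. With 10% dropout, 28/0.9 = 31.1, hence 32 (16 per group). The figure reproduces and supplies the n below. The pre/post comparisons have no sample-size figure of their own.

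**2. What each comparison estimates.** Let L be the shared change from day 1 to day 7, M the shared change from day 7 to week 3, and D1, D2, D3 the diet effect after 1, 2 and 3 weeks.

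| Comparison | Expectation |
|---|---|
| MCT-KD, day 1 to day 7 | L + D1 |
| SAD, day 1 to day 7 | L |
| Pooled, day 1 to day 7 | [16(L + D1) + 16L]/32 = L + D1/2 |
| Between arms, day 7 | D1 |
| MCT-KD, day 1 to week 3 | L + M + D3 |
| SAD, day 1 to week 3 | L + M + D2 |
| Pooled, day 1 to week 3 | L + M + (D2 + D3)/2 |
| SAD, day 7 to week 3 | M + D2 |

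This is algebra and holds for any size of L. With L = 0 and D1 = 0.5, the pooled week-1 value is 0.25, half the effect. With L = 0.3 and D1 = 0.5 it is 0.55. With L = 0.3, M = 0 and D2 = 0.5, SAD gives 0.8 from day 1 and 0.5 from day 7.

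**3. Illustrative false-positive rates.** The documents give no value for L, so L is assumed, in units of the SD of the change. There is no diet effect and M = 0. The test is a one-sample t-test of change at two-sided 0.05, with noncentrality L√n. At L = 0.3, for example, this is 0.3 × √32 = 1.70 pooled and 0.3 × √16 = 1.20 in SAD.

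| L | Pooled, n = 32 | SAD day 1 to week 3, n = 16 |
|---|---|---|
| 0 | 5% | 5% |
| 0.2 | 19.5% | 11.6% |
| 0.3 | 37.6% | 20.3% |
| 0.5 | 78.2% | 46.5% |

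A 20,000-run simulation gave 37.9% and 78.7% for the pooled test at L = 0.3 and 0.5. The between-arm test stayed at 5.2% and 5.0%.

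If L is stated in SDs of the outcome with test-retest correlation ρ, divide by √(2(1 − ρ)). At ρ = 0.5 the table is unchanged. At ρ = 0.7 an L of 0.3 becomes 0.3/0.775 = 0.387, and the rates are 56.5% pooled and 30.6% in SAD.

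SAD day 7 to week 3 is at 5% when M = 0. It rises to 7% to 11% if M is 0.1 SD of the outcome (ρ 0.5 to 0.85), so a day-7 baseline removes L but not M.

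**4. Would one mixed model rescue a pooled estimate?** Take a model with subject and visit terms and one ketogenic indicator (MCT-KD 0, 1, 1; SAD 0, 0, 1). Assume D1, D2, D3 = 0.2, 0.4, 0.5 SD.

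- Between-arm differences by visit are 0, 0.2 and 0.5 − 0.4 = 0.1; centred, −0.1, 0.1, 0.
- Indicator differences are 0, 1, 0; centred, −1/3, 2/3, −1/3.
- Slope = (0.0333 + 0.0667 + 0)/(1/9 + 4/9 + 1/9) = 0.1/0.667 = 0.15 SD.

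This is below all three true effects, because growth with time on diet is absorbed by the week-3 visit term.

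**The case against.** Several counter-arguments carry weight.

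- **No test is named.** Section 9.4.3 specifies ANCOVA and longitudinal models, not a paired test on pooled changes. So the rates in step 3 are not properties of the plan. The expectations in step 2 still hold for any analysis of change from day 1 without a control contrast.
- **The exposure is disclosed.** Section 1.1 itself records 0 weeks of ketogenic diet for SAD at week 1 and also compares the arms separately, so SAD's own change displays the shared one. A reader might infer that the pooled change will be credited to the diet; no section says so. What stands is that the comparison is labelled pre versus post intervention.
- **The sentence is loose.** It also says the groups combine into one ketogenic group at week 3, so the pooling could be meant for week 3 only. Pooling at both times is the natural reading, not the only one. The week-3 problem remains on either reading.
- **Day 1 is not the pre visit throughout.** A reader might take section 4.1 as covering every outcome. But its Geriatric Depression Scale paragraph uses screening, and the schedule in section 1.3 shows NMSS, PDQ-39 and total UPDRS at screening and week 3 with no day-7 value. For EEG, section 1.1 lists day 1, day 7 and week 3, so the SAD step from day 7 is already available.
- **Section 4.2 has a second safeguard.** It would compare tests more and less prone to learning to judge whether learning is operating. That helps interpretation but takes nothing out of the estimates. Simple reaction time, one of the less exposed tests, is not in section 1.1's list for these comparisons.

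**Conclusion.** The point holds for the exploratory pre/post comparisons only. Read naturally, the pooled week-1 comparison estimates all of the shared inpatient or practice change and half of the diet effect. SAD's week-3 change from day 1, and the pooled week-3 change, include the six-day standard diet. Randomisation removes the shared change only from between-arm contrasts.

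The structure follows from the stated visits and the 16:16 allocation. The size does not: L is unknown, and every false-positive rate above rests on an assumed L, an assumed test and no shared change after day 7. The error can go either way, since the pooled week-1 value exceeds D when L is larger than D/2 and falls short when it is smaller.

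A reader might go on to doubt the trial's main results. The documents do not support that: the feasibility composite, the day-7 TUG contrast, the day-7 between-arm ANCOVA and the sample size are untouched. This is a minor-to-moderate point, worth correcting because the remedy needs only wording.

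**What to change.** Amend sections 1.1, 4.1 and 9.4.3.

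1. Remove all participants from the week-1 pre/post comparison. Make the between-arm day-7 ANCOVA the week-1 test of the diet, and report within-arm day-1-to-day-7 changes descriptively.
2. For outcomes measured on day 7, define SAD's pre visit for the week-3 comparison as day 7; day 1 stays for MCT-KD. Label the within-arm and pooled week-3 changes as descriptive and uncontrolled, because later learning and the move from hospital to home remain confounded with diet.

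Do not substitute the single-indicator mixed model as the pooled estimate. It assumes a constant diet effect, contrary to Hypothesis B, and is biased if the effect grows with time on diet (step 4).

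Cost: no new visits or data. The SAD comparison covers two weeks rather than a nominal three, intervals are wider than for a naive pooled test, and outcomes without a day-7 value cannot use the new baseline.

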1.2 SCHEMA

Abbreviated Title: Tolerability and efficacy of ketogenic diet in Parkinson's Disease

Version Date: 04/19/2021

1.3 SCHEDULE OF ACTIVITIES (SOA)

Procedures	Screening/ enrollment *	Day 1 (pre- intervention)	Day 2 (diet started)	D 3	D 4	D 5	D 6	D 7	W 3 (post)
Fill out intake form and determine eligibility	X								
Pregnancy test**	X								
Informed consent	X								
Randomization to Ketogenic Diet or Usual Diet group, stratified 2-factor covariate	X								
anthropomorphic measures (height, weight, abdominal circumference)	X							X	X
Vital signs, including orthostatic (exploratory outcome)	X	X	X	X	X	X	X	X	X
History and Physical Exam	X	X							
Focused Neurologic Exam	X	X							X
Bioelectric Impedance (BIA)	X								X
MOCA	X								
Screening BMP (to establish eGFR), hepatic panel, lipid panel, A1C, beta-HCG if female < age 60	X								

Abbreviated Title: Tolerability and efficacy of ketogenic diet in Parkinson's Disease

Version Date: 04/19/2021

Procedures	Screening	Day 1	Day 2	Day 3	Day 4	Day 5	Day 6	Day 7 / Post	W 3 (post)
UPDRS part 3	X	X	X	X	X	X	X	X	X
Total UPDRS	X								X
Hoehn & Yahr Stage	X								
Electrocardiogram (ECG)	X*	*(If ECG service is unable during screening, may be performed on Day 1 prior to initiation of diet)							
metabolic labs (A1c, insulin, CRP, apolipoprotein panel, HOMA-IR, cortisol, TSH, T3, free T4), BDNF (exploratory outcome), lipid panel (day 7, week 3), A1c (week 3 only)		X						X	X
Non Motor Severity Scale (NMSS) (exploratory outcome)	X								X
PDQ-39 questionnaire (exploratory outcome)	X								X
Resting heart rate variability (2-10 min)		X	X	X	X	X	X	X	X

Abbreviated Title: Tolerability and efficacy of ketogenic diet in Parkinson's Disease

Version Date: 04/19/2021

Procedures	Screening	Day 1	Day 2	Day 3	Day 4	Day 5	Day 6	Day 7 / Post	W 3 (post)
(exploratory outcome)									
Cardiovascular testing – Valsalva maneuver, deep breathing (exploratory outcome)		X						X	X
Timed up and Go (TUG) AM fasting (secondary outcome)	X	X	X	X	X	X	X	X	X
Simple reaction time (SRT) daily (exploratory outcome)		X	X	X	X	X	X	X	X
9-hole pegboard test (9-HPT) daily (exploratory outcome)		X	X	X	X	X	X	X	X
daily journal of ON/OFF and keto-induction symptoms, (Likert scales) and mood (exploratory outcome)		X	X	X	X	X	X	X	X
EEG spectral analysis and connectivity analysis (phase lag index) days 1, 7 (exploratory outcome)		X						X	X
Respiratory Metabolic Cart quotient (pCO ₂ , :pO ₂) for resting and energy expenditure	X								X
BMP, magnesium		X		X	X	X	X	***	

Abbreviated Title: Tolerability and efficacy of ketogenic diet in Parkinson's Disease**Version Date:** 04/19/2021

POG glc checks		X	X	X	X	X	X	X	
Beta-OHB level twice daily, except once on day 7****		X	X	X	X	X	X	X	X**** *
Procedures	Screening	Day 1	Day 2	Day 3	Day 4	Day 5	Day 6	Day 7 / Post	W 3 (post)
Plasma dopamine twice daily		X	X	X					
Continuous glucose monitoring (Precision Libre Pro)		X	X	X	X	X	X	X	
n-back working memory test daily (exploratory outcome)		X	X	X	X	X	X	X	X
Stroop word color interference test daily (exploratory outcome)		X	X	X	X	X	X	X	X
MN and PQ keyboard tasks		X	X	X	X	X	X	X	X
Safety monitor (telephone interview) survey 2-4 weeks post-study completion									X
Depression screening tool: Geriatric Depression Scale (GDS)	X							X	X
Gastrointestinal motility / symptoms diary (daily days 1-7)		X	X	X	X	X	X	X	

Abbreviated Title: Tolerability and efficacy of ketogenic diet in Parkinson’s Disease

Version Date: 04/19/2021

Gastrointestinal Symptom Rating Scale	X	X						X	X
Exit Survey acceptability of ketogenic diet									X
Tracking diet via unscheduled calls*****	X								X
*No Day 0 (7 days of baseline diet and history, then Day 1 is first day of admission) **women of childbearing potential ***repeat BMP and magnesium on days 6 and 7 if abnormal in prior days ****check beta-OHB in fasted state at week 3 visit ***** To occur during week between screening visit/enrollment and day 1 of admission and during 2 weeks after day 7. See Section 4.1 for details.									

Abbreviated Title: Tolerability and efficacy of ketogenic diet in Parkinson's Disease

Version Date: 04/19/2021

